intake; 7) Given the high rates of IPV among women who seek mental health treatment, mental health treatment settings compared to other medical settings (e.g. primary care) are more effective sites for focused case finding and interventions.

Despite the need, recent research suggests that there are low screening and intervention rates of female mental health patients with IPV by mental health providers psychiatrists hold less supportive attitudes towards IPV victims than other physicians, IPV training and knowledge of resources is limited among psychiatric residents, and mental health professionals find enquiry about domestic violence difficult because of their lack of knowledge and expertise in this area and/or because they do not think it is part of their role. As researchers have noted, there are much needed but inadequate systems in place for mental health clinics or providers to respond to women with IPV. Virtually no empirically-based interventions exist that address IPV among mental health treatment-seeking perinatal women. Women in the perinatal period were selected for two primary reasons: (a) interventions at this juncture may take advantage of a particularly salient point in a woman's life, in which she may be more open to considering behavior change; and (b) any positive change made has the possibility of a dual impact, on the woman's life as well as that of her infant. The proposed project will test an innovative, high-reach, easily implementable, low-cost computer-delivered intervention, Reach Out for a Safe Environment (ROSE), which is theoretically driven and addresses known barriers in early intervention with at-risk women throughout the perinatal period. Preliminary data from our pilot study provide reassurance that ROSE will successfully reduce IPV in our target population. A fully powered RCT trial of ROSE is necessary to determine efficacy. A cost estimate in a real-life clinical setting will provide information to facilitate implementation and dissemination.

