### Aim 2 (Secondary Outcomes)

- (a) ROSE, as compared to control, will result in greater positive affect and well-being at 6-weeks, 3, 6- and 12-months follow up;
- (b) ROSE, as compared to control, will result in greater perceived emotional support at 6-weeks, 3, 6- and 12-months follow up;
- (c) For future implementation and dissemination, we will estimate the resources needed and costs to deliver ROSE. Additionally, we will estimate the incremental cost effectiveness of ROSE compared with treatment as usual.

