**Costs:**

A secondary aim of this study will be to measure the total costs of ROSE vs. usual care for those at risk of IPV at participating study sites. Adhering to Second Panel on Cost-Effectiveness in Health and Medicine Guidelines[68], we will perform a cost-effectiveness analysis (CEA) to estimate the cost per IPV incident prevented by ROSE. Cost will be measured relative to usual care, with IPV reduction proxied by comparison to the research assistant blindable control condition that should be equivalent to usual care. We will collect data on three types of costs: 1) Implementation costs of establishing the ROSE program in a mental health clinic, including staff training time and resources, costs of hardware, software licensing, and adaptation of the program content to be relevant to the location; 2) Operational costs, including the human labor involved in identifying eligible patients, conducting screening, introducing patients to the program and demonstrating how to use it, obtaining follow-up information, and conducting the booster call, and 3) Participant costs in terms of time spent at the intervention and booster session, plus any travel costs related to intervention attendance, beyond the session where the person was screened. To record the first two sets of costs and distinguish them from research activities, the research assistants and the interventionist will track and log times for all study activities. The third set of costs will be captured by including questions about travel/waiting time, occupation, wage rate, and out-of-pocket expense in the survey at each added visit.

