#### Adequacy of protection against risks

At each point of contact in the studies, participants will be reminded of the alternative of not participating in the study (or once enrolled, to discontinue participation), and will be informed that their care at The Center for Women's Behavioral Health at Women and Infants Hospital and in any other follow-up medical care will in no way be affected by their decision to participate or not to participate in the study. Moreover, we will provide referral information to all participants at each point of contact. We will also remind participants that they should only keep handouts related to the study if they feel it is safe to do so. If they feel that it may be unsafe to keep any handouts, participants will be advised to discard these prior to leaving the assessment/intervention session. Further procedures to minimize each of these risks are described below.

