For the duration of the study, if a woman discloses that she is in an abusive relationship, she will be provided with the battered women's crisis line for emergencies, referrals to battered women's shelters, and told how to obtain a restraining order. If the partner of the participant is also abusing her child[ren], the research staff person involved will let the woman know that she has a choice to make, either she herself will call child welfare or the research staff will report the concern. She will be reminded that she as the mother is responsible for protecting her child[ren] and if her partner hurts them and she fails to call child welfare or the police, she could be charged with neglect and her children could be taken away. However, the woman must determine if calling child welfare herself will place her at further risk from the abuser. The research personnel involved will also remind the woman that if she calls herself, child welfare is more likely to view the woman favorably under these circumstances. The research personnel involved will provide the woman with the relevant phone number/s. The research personnel involved will let the woman know that let she will be calling child welfare herself because it is the law. This same procedure will be followed for any other case of suspected child abuse.

*Potential benefits of the proposed research to the subjects and others*

The potential benefits to women participating in this study include participants' increased awareness of resources for IPV. Half of the participants in this study will not receive any form of intervention, and thus are unlikely to receive any direct health benefit; however, women in both conditions will receive a list of referrals and community resources for IPV. Furthermore, the treating mental health providers of women who screen positive for IPV will (with the women's consent) be provided a print-out of women's survey responses. Half of the participants will receive a brief intervention designed to increase the likelihood of self-change and/or obtaining resources for IPV.

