**Costs:** RAs, interventionist, training, and supervisory time will be priced based on actual salaries, plus fringe benefits and overhead (drawn from institutional records), with sensitivity analysis on salaries at average wage rates for job titles nationally based on Bureau of Labor Statistics (BLS) annual Occupation and Employment Survey (OES) data. Participant time will be priced at the participant's hourly wage, with the state minimum wage used to price time of those who are not presently employed. This pricing approach is widely accepted[80]. Because treatment as usual has no cost and the incremental costs of treatment are directly measurable, power to detect a difference is not a consideration; the standard error of the added costs can be calculated directly and cannot overlap with \$0. Data from different years will be adjusted to same-year dollars using the appropriate Employment Cost Index from BLS for wages and the Consumer Price Index for other costs. The cost-effectiveness ratio will be computed as number

of IPV incidents prevented divided by total cost. To judge the CEA estimate, we will compare it to the average cost of an IPV incident. Bid economist [name] is about to submit a manuscript updating IPV costs based on recent data and an amalgam of his prior estimates and estimates for the Centers for Disease Control[81,82]. Our cost of an IPV includes the quality-adjusted life years lost to the incident, so it can be used to estimate a second cost-effectiveness ratio, namely the cost per quality-adjusted life year saved. The numerator in that calculation is intervention costs minus the medical and other direct (criminal justice) costs of the incident. The IPV costs include lifetime costs related to medical care and criminal justice, converted to present value using the 3% discount rate recommended by the PCEHM[68]. We will use the Crystal Ball® add-in to Excel to bootstrap standard errors for the cost-effectiveness ratios. We also will conduct one-way sensitivity analyses on non-probabilistic parameters, notably the discount rate and the wage rates of the clinical staff. NB: a much larger sample would be needed to directly track the cost of the IPV incidents.

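### The Aim 2c cost-effectiveness ratio rests on an untested assumption, in tension with the rest of the protocol, that a screened and repeatedly referred control arm is equivalent to usual care

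*Combined protocol and SAP*

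**What the plan says.** The objective, under Aim 2 (Secondary Outcomes), is: "we will estimate the incremental cost effectiveness of ROSE compared with treatment as usual".

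The Costs paragraph in section 2 sets the two halves of the ratio:

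- Cost: "Cost will be measured relative to usual care". Operational costs charged to ROSE include "the human labor involved in identifying eligible patients, conducting screening".
- Effect: "IPV reduction proxied by comparison to the research assistant blindable control condition that should be equivalent to usual care".

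The Costs paragraph in section 4 sets the comparator's cost at zero: "Because treatment as usual has no cost and the incremental costs of treatment are directly measurable". It names the discount rate and clinical staff wages as the parameters for one-way sensitivity analysis.

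On what control women receive, Adequacy of protection against risks says "we will provide referral information to all participants at each point of contact". The potential-benefits paragraph under Protection against risk says "women in both conditions will receive a list of referrals and community resources for IPV". The same section gives any woman who discloses an abusive relationship a crisis line, shelter referrals and restraining-order information, and allows survey responses of women who screen positive to go to their provider with consent. Recruitment Methods and Informed Consent Process makes a positive IPV screen a condition of entry and offers IPV resources to every eligible woman.

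On ordinary practice, Background says "there are low screening and intervention rates of female mental health patients with IPV by mental health providers".

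**The concern.** The ratio compares ROSE with usual care on cost and with the control arm on effect. These are the same comparison only if the control arm has the same IPV outcome as usual care. By the protocol's own account, control women receive IPV screening, resources and repeated referral, which Background suggests many women in ordinary care do not.

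The consequence is asymmetric. Identification and screening labour enters ROSE's cost in full, because usual care is priced at zero. Anything that screening and referral achieve is present in both arms, so it drops out of the effect. ROSE pays for screening and gets no credit for what screening may do.

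This matters because section 4 judges the result against the average cost of an IPV incident, and Data checking says the aim is to see whether cost-effectiveness is favourable enough. An overstated cost per incident could put a worthwhile programme on the wrong side of that benchmark, and no planned analysis would show how far the assumption drove the result.

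**Working it through.** The documents give no cost-effectiveness ratio, unit cost, incident count or usual-care IPV rate, so there is no planned figure to reproduce. What can be derived is how the ratio depends on the assumption.

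**Inputs**

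- C: cost of ROSE against usual care, including identification and screening labour (Costs, section 2), with usual care at zero (Costs, section 4).
- E_UC, E_C, E_R: IPV incidents under usual care, control and ROSE.
- s: the share of ROSE's effect against usual care that screening and referral deliver in the control arm. It is not in the documents, so the values below are assumptions.

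I use cost per incident prevented, as the section 2 Costs paragraph does. Section 4 writes the ratio the other way up (incidents over cost), which needs separate correction; on that scale the factors below are inverted.

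**Step 1: the two ratios**

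- Ratio for the stated objective: C / (E_UC − E_R).
- Ratio as planned: C / (E_C − E_R).

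**Step 2: relate them**

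Let D = E_UC − E_R. By definition of s, E_UC − E_C = sD, so E_C − E_R = (1 − s)D. Then planned / target = [C / ((1 − s)D)] / [C / D] = 1 / (1 − s).

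**Step 3: put in a range**

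| Assumed s | Planned / target |
|---|---|
| −0.10 | 1/1.10 = 0.91 |
| 0 | 1.00 |
| 0.10 | 1/0.90 = 1.11 |
| 0.25 | 1/0.75 = 1.33 |
| 0.50 | 1/0.50 = 2.00 |

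The ratio would flatter ROSE only if control women did worse than usual care (negative s).

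**Step 4: effect on the decision**

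Let T be the average cost of an IPV incident. The planned ratio exceeds T whenever the target ratio exceeds (1 − s)T. A programme with a target ratio between (1 − s)T and T would be judged wrongly: between 0.90T and T at s = 0.10, 0.75T and T at s = 0.25, 0.50T and T at s = 0.50.

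**Step 5: the ratio per quality-adjusted life year**

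With q life years and m direct costs per incident, the target is (C − mD)/(qD) = C/(qD) − m/q. The planned version is C/((1 − s)qD) − m/q. Only the intervention-cost term is inflated by 1/(1 − s).

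**Step 6: a matched comparison**

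If a share c of C is common to both arms, the ratio of ROSE against the trial's control is (1 − c)C / ((1 − s)D). The planned ratio is 1/(1 − c) times this: 1.11, 1.33 or 2.00 for assumed c of 0.10, 0.25 or 0.50. This is the gap between two different questions, not an error in the usual-care ratio. Its size is unknown until the activity logs are in.

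**The case against.** The strongest defence is that the proxy is declared. The plan names one target, usual care, for both terms and says openly that the control stands in for it. If the two are equivalent, the ratio answers Aim 2c. That stands. A reader might infer that the ratio cannot answer its objective at all; the documents do not support that, because at s = 0 the ratio is valid.

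Nor is there evidence in the documents that screening and referral reduce IPV. The control session is entertainment content chosen to have little therapeutic effect, the potential-benefits paragraph says this half receives no intervention, and the section on including a diverse population notes that few IPV interventions have worked in perinatal women. Some of the extras depend on interest or consent. This keeps s open, including at zero. But the inert content concerns the session only, and the statement about no intervention is followed directly by the one about referrals and resources in both arms.

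Usual practice at the two clinics is not described. Background cites general literature on providers, and also a chart review of 299 perinatal women in mental health treatment in which current victimization was recorded, so some clinics already ask. The gap between control and usual care at these sites is therefore uncertain, which is a reason to vary the assumption.

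Screening labour is a real incremental cost for a clinic that must start screening. A reader might infer that ROSE's cost is overstated in every case; that holds only for a ROSE-versus-control ratio, which the plan does not propose.

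A reader might also try to size the shared cost from the 5 to 10 minute screening survey and the prevalence figures in Background. That is not reliable. The survey covers general health, diet, smoking and internet access as well as eligibility; the prevalence figures do not use the trial's entry criterion (a score of 4 or more on the screening tool); and the full cost base includes training, hardware, licensing, demonstration and participant time.

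Finally, section 4 introduces its sensitivity analyses with a word that leaves the list open. Others are possible, but none on equivalence is named.

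**Conclusion.** The concern holds in a limited form. The ratio depends on an equivalence that is asserted without justification, conflicts with the protocol's account of what control women receive and of ordinary care, and is not among the named sensitivity analyses. The overstatement of cost per incident prevented is 1/(1 − s), or 11%, 33% and 100% for assumed s of 0.10, 0.25 and 0.50. The bias is conditional: zero if screening and referral do nothing, and against ROSE, hence conservative, if they help.

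The derivation assumes that screening and referral work alike in both arms and that C is measured as planned. The issue touches one secondary economic aim and not the efficacy or safety comparisons.

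**What to change.** 1. Add a matched trial-based ratio of ROSE against the control condition, labelled IPV screening plus referral. Use the activity logs already planned to remove costs common to both arms: identification, screening, resource provision and follow-up contacts. ROSE's own session and booster stay in. Treat the control's entertainment session and call as attention matching for research, not as an offset to ROSE's cost.
2. Keep the usual-care ratio with full costs including screening. State that it depends on the control being equivalent to usual care, and that it is conservative if screening and referral help.
3. Add a one-way sensitivity analysis over s to those in the section 4 Costs paragraph, for example 0 to 0.50, and report the value of s at which the conclusion against the average incident cost would change.
4. Describe usual IPV screening and referral at the two clinics, so that readers can judge which values of s are plausible.

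The cost is some added wording, a re-split of logs already planned and a little more analysis. The sponsor keeps its question but accepts a qualified label for the comparison with treatment as usual. Replacing the usual-care question outright is not needed.

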**Exploratory Potential Mediators:**

We hypothesize that self-efficacy and empowerment will mediate the relationship between the effects of ROSE and the presence of IPV (see Figure 2).

1. *Empowerment* will be measured using the Personal Progress Scale-Revised (PPS-R[69]) for assessing skills, social supports, and resources to cope more effectively with relationship stress and trauma. PPS-R is often used to evaluate empowerment-based interventions. The measure has shown good reliability and validity[69].
2. *Self-efficacy* will be assessed with the General Self-Efficacy Scale, a 10-item self-report measure[70]. It measures personal competence to deal effectively with a variety of stressful situations. The scale has been found to be reliable, homogeneous, and unidimensional across 25 nations[71].

**Perinatal Depression:**

At all follow-up assessments, participants will be screened for perinatal depression because the majority of women seen at both sites report perinatal depression and perinatal depression is strongly associated with IPV [72,73]. Any participant who screens positive for postpartum depression (The Pregnancy Risk Assessment Monitoring System 6 (PRAMS-6) score of 17 or more) will be referred for appropriate local clinical care [74].

Danger Assessment (DA)-5. The DA-5 was developed for use in healthcare settings, including emergency and urgent care settings to evaluate the risk of an intimate partner violence victim being killed, nearly killed or severely injured by an intimate partner [59]. The DA-5 was found to have adequate validity and is recommended for a quick assessment of homicide or near homicide risk among IPV survivors [59]

(See Protection of Human Subjects).

**Data Collection at the University of Michigan Site**

The University of Michigan site is the other site in this study. This site will be conducting the same data collection procedures. This site will send de-identified data to the Women and Infants site to be analyzed. The Women and Infants site will not send any data to the University of Michigan site.

**Table 1: Study Measures**

	Intake	6-weeks	3-months	6 months and 12 months
Self-report Measure				
Demographics and IPV information	X	X	X	X
Composite Abuse Scale	X	X	X	X
Positive Affect and Well-being	X	X	X	X
Perceived Emotional Support	X	X	X	X
Personal Progress Scale-Revised	X	X	X	X
General Self-efficacy Scale	X	X	X	X
Edinburgh Postnatal Depression Scale		X	X	X
COVID-19 Family Stress Screener	X	X	X	X
Economic Measure				
Cost Analysis	X	X	X	X

### 3. RISKS AND BENEFITS

#### Potential risks

There are five potential low- to moderate-risks to subjects associated with this research project:

Breach of confidentiality: Assessment procedures could reveal sensitive information about participants' medical history and history of IPV. Risk of breach of confidentiality is possible, though highly unlikely. Specifically, if a participant tells research staff that she is planning to harm herself or her children, the research staff will report this information to the appropriate agency, as required by law. Other than the need to report those incidents that are regulated by mandatory reporting laws, we feel that there is minimal risk to participants with regard to other breaches in their confidentiality.

Coercion: Coercion occurs when potential participants feel compelled to participate in research for reasons such as perceived demand or the availability of large sums of reimbursement. This can be particularly true when there is little benefit to the individual for their participant (not an issue in this study). In the present study, the inclusion of a protected population and protection from coercion is of the utmost importance.

Discomfort: Participation in the study may lead to psychological distress due to the sensitive nature of questions regarding disclosure of IPV during the perinatal period and the related negative social and psychological consequences.

Study-related partner violence: Participants who return to or continue to have contact with their abuser may be at increased risk for abuse if he or she were to find out about the woman's participant in the research project.

Social or legal consequences: Possible social or legal consequences due to revelations of IPV during the perinatal period.

#### Adequacy of protection against risks

At each point of contact in the studies, participants will be reminded of the alternative of not participating in the study (or once enrolled, to discontinue participation), and will be informed that their care at The Center for Women's Behavioral Health at Women and Infants Hospital and in any other follow-up medical care will in no way be affected by their decision to participate or not to participate in the study. Moreover, we will provide referral information to all participants at each point of contact. We will also remind participants that they should only keep handouts related to the study if they feel it is safe to do so. If they feel that it may be unsafe to keep any handouts, participants will be advised to discard these prior to leaving the assessment/intervention session. Further procedures to minimize each of these risks are described below.

